# **6.3 Missing Data**

Missing data are expected at follow-up time points (3 months and 6 months) in primary and secondary outcomes. Assuming that the missing data follow a Missing at Random (MAR) pattern, Multiple Imputation by Chained Equations (MICE) (Van Buuren and Groothuis-Oudshoorn 2011) will be used to handle missing values for the primary outcome and secondary outcome adjusting all baseline covariates. Imputations will be generated with 15 datasets using the "mice()" function from the "mice" package in R. The imputation methods will include predictive mean matching (pmm) for continuous outcomes, logistic regression (logreg) for binary outcomes, and polytomous regression (polyreg) for categorical outcomes. Each imputed dataset will be analyzed separately, and results will be combined using Rubin's Rules(Rubin 2004) to obtain pooled estimates and confidence intervals, accounting for the variability within and between imputations.

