# **4.3 Baseline Patient Characteristics**

Baseline characteristics will be summarized with descriptive statistics, including study site, age, sexual identity, outness, relationship status, high school location, ethnicity, education level, occupation, income, previous PrEP usage, and current PrEP status.

To assess baseline balance between the groups, we will calculate the Absolute Standardized Difference (ASD) for each characteristic.

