#### 6.2 Analysis Methods

We will use Generalized Linear Mixed Models (GLMMs) to handle the various types of outcomes across primary and secondary measures, which allows for fixed effects (intervention, site, time, baseline outcome, the interaction between intervention and time baseline covariates) and random effects (including participant-level variability). The adjusted covariates include age, relationship status, and PrEP usage. All analyses will be conducted in R. The general form of the GLMM is:

$$g(\mu(Y_{ij})) = \beta_1 I(Time_{ij} = 3) + \beta_2 I(Time_{ij} = 3) \times Intervention + \beta_3 I(Time_{ij} = 6) + \beta_4 I(Time_{ij} = 6) \times Intervention + \beta_5 Covariates_i + \mu_i + \epsilon_{ij}$$

 $Y_{ij}$  represents the outcome for participant i at time j,  $\mu(Y_{ij})$  is the expected value of  $Y_{ij}$  given the covariates,

g(.) is the link function that relates the linear predictors to the expected value of outcome (e.g., logit link for binary outcomes, identity link for continuous outcomes),

 $\beta_1$  is the effect of time at 3 month,

 $\beta_2$  is the interaction effect between intervention and time at 3 month,

 $\beta_3$  is the effect of time at 6 month,

 $\beta_4$  is the interaction effect between intervention and time at 6 month,

 $\beta_5$  is the covariate effect,

 $\mu_i$  is the random intercept for each participant, where  $\mu_i \sim N(0, \sigma_i^2)$ ,

I(.) is the indicator function.

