# **Primary Outcome**

The primary outcome, PrEP adherence obtained through DBS, is a binary variable and will be analyzed using a GLMM with a logit link function. The intervention effect will be represented by an adjusted odds ratio, and will be assessed across different follow-up points. This analysis will be implemented in R using the "glmer()" function, specifying a logit link and a random intercept for participants to account for within-subject correlations.

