### **Secondary Outcomes**

The secondary outcomes include continuous, binary, and categorical variables, each analyzed with an appropriate link function based on the outcome type. For continuous outcomes, such as depression and anxiety symptomology scores, an identity link function will be used, estimating the intervention effect as the difference in mean scores between groups. This model will be implemented using the "lmer()" function in R. Binary secondary outcomes, will use the same logit link function and implementation details as the primary outcome analysis.

**Table 1.** List of secondary outcomes.

Variable coding
Continuous
Binary and continuous
Continuous
Continuous
Binary
Ordinal categorical, with 7 categories

PrEP stigma	Continuous
Positive attitudes/beliefs	Continuous
about PrEP	
Negative attitudes/beliefs	Continuous
about PrEP	
PrEP barriers	Continuous
PrEP facilitators	Continuous
STI diagnoses	Binary
CAS acts	Continuous

Each model will output the intervention effect at baseline, 3 months, and 6 months (with the exception of STI diagnoses and CAS acts, which are only measured at baseline and 6 months as well as DBS and self-report PrEP adherence, which are only measured at 3 months and 6 months), with 95% confidence intervals to provide estimates of precision.

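### SAP 6.3 does not put randomised arm or the other visit's outcome in the imputation model; taken literally, it shrinks the arm difference by about the missing fraction

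*SAP*

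**What the plan says.** SAP 6.3 assumes data missing at random and plans 15 imputations with mice(), pooled by Rubin's rules. The only conditioning set it names is in the statement that the method "will be used to handle missing values for the primary outcome and secondary outcome adjusting all baseline covariates". Imputation methods are assigned by variable type: "predictive mean matching (pmm) for continuous outcomes, logistic regression (logreg) for binary outcomes". There is no predictor list, no imputation by arm, and no statement of wide (one row per man) or long (one row per visit) layout.

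SAP 6.2 describes the analysis model as having "fixed effects (intervention, site, time, baseline outcome, the interaction between intervention and time baseline covariates", and then states: "The adjusted covariates include age, relationship status, and PrEP usage". Intervention is thus listed apart from the covariates. For the primary outcome, "The intervention effect will be represented by an adjusted odds ratio, and will be assessed across different follow-up points", using glmer() with "a random intercept for participants to account for within-subject correlations". Section 6.2 also notes the exception for "DBS and self-report PrEP adherence, which are only measured at 3 months and 6 months", so DBS has no baseline value that could stand in for the other visit.

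**The concern.** An imputation model should contain at least the terms whose effects the analysis will estimate. Here those are arm at each visit and the correlation between a man's two visits.

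Because of randomisation, baseline covariates carry essentially no information about arm. If they are the only predictors, missing values in both arms are drawn around the same pooled rate, so the imputed men show no arm difference and dilute the observed one. Rubin's rules cannot reveal this, because every imputed dataset has the same fault. Section 6.3 applies the method to the primary and secondary outcomes alike, and 3.3 says the trial's estimates are to inform a later effectiveness trial.

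Omitting the other visit is a different fault. Imputed visits then carry no within-man correlation, so the fitted random-intercept SD falls, and with it the scale of the conditional odds ratio.

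A linked gap is that binary DBS (primary) and continuous DBS (secondary) come from the same assay but are given separate imputation methods, with no stated link at 1000 fmol/punch.

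**Working it through.** **Inputs.** SAP 3.3: 94% vs 85% adherent at 3 months, 92% vs 86% at 6 months, 60 men per arm, retention of about 89% in prior trials. Assumed: 11% missing (1 − 0.89, a proxy for DBS completeness), equal in both arms and completely at random. Random-intercept SDs of 1, 2 and 3 are also assumed; the documents give none.

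**The plan's own figure.** 0.06/0.32 = 0.1875. From the rates, SD = √[(0.92×0.08 + 0.86×0.14)/2] = 0.311 and 0.06/0.311 = 0.193. Both round to the stated 0.19. The SAP gives no figure for imputation bias.

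**Literal reading: arm and other visit omitted.** With missing fraction m and pooled rate p̄, the rate in each arm after imputation is (1 − m)p + m·p̄, so the difference becomes (1 − m) times the true difference.

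- 6 months, p̄ = 0.89. Control: 0.89×0.86 + 0.11×0.89 = 0.8633. Intervention: 0.89×0.92 + 0.11×0.89 = 0.9167. Difference 5.34 points instead of 6.0; marginal odds ratio (OR) 1.74 instead of 1.87.
- 3 months, p̄ = 0.895. Rates 0.8549 and 0.9351. Difference 8.01 points instead of 9.0; OR 2.44 instead of 2.76.
- 6 months at 7% or 14% missing (the 93% and 86% retention figures in the protocol's Retention text): 0.93×6.0 = 5.6 points (OR 1.79) or 0.86×6.0 = 5.2 points (OR 1.71).

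**Against the standard error.** SE of the 6-month difference = √(0.86×0.14/60 + 0.92×0.08/60) = 5.69 points. The bias is 0.66/5.69 = 0.12 SE.

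**Planned conditional OR.** For each assumed SD, I took the joint distribution of the two visits from a random-intercept logistic model with the 3.3 marginal rates, mixed in the imputed men, and refitted the arm-by-visit effects and the SD by maximising the expected log-likelihood (no covariates). At 6 months, with arm and other visit omitted:

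| SD | True OR | Same men miss both visits | Visits missed independently |
|---|---|---|---|
| 1 | 2.00 | 1.84 (log-OR −12%) | 1.82 (−13%) |
| 2 | 2.43 | 2.11 (−16%) | 2.05 (−19%) |
| 3 | 3.14 | 2.50 (−20%) | 2.35 (−25%) |

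With a true SD of 2.00, the fitted SD is 1.83 (same men) or 1.68 (independent).

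**mice() defaults on long data that contain arm.** Arm and visit enter as main effects only, so the arm-by-visit term is missing as well as the other visit's outcome. A main-effects logistic fit to the four 3.3 rates gives imputed arm gaps of 7.34 points at 3 months and 7.66 at 6 months.

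- 3 months: 0.89×9.0 + 0.11×7.34 = 8.82 points.
- 6 months: 0.89×6.0 + 0.11×7.66 = 6.18 points.

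The two visits are pulled towards each other. The 6-month conditional log-OR then ranges from a 2% gain (SD 1, same men) to a 12% loss (SD 3, independent).

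**Wide data with arm and both visits.** No shrinkage arises.

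**DBS link.** If binary and continuous values were drawn independently at a pooled adherence rate of 0.89, then 2×0.89×0.11 = 19.6% of imputed visits would contradict the cut. That is about 2.6 of the 0.11×120 = 13.2 men missing per visit.

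**The case against.** Section 6.3 does not say that baseline covariates are the only predictors. By default mice() uses every other column supplied, so arm is lost only if the analyst leaves it out of the data or the predictor matrix. A reader might infer that the SAP prespecifies an imputation without arm. The documents do not support that: they are silent, and the code may well include it. What stands is that the text as written names one set without arm, and that the layouts it permits give different answers.

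Nor can much be drawn from arm being absent from the list in 4.3 ("including study site, age, sexual identity, outness, relationship status, high school location, ethnicity, education level, occupation, income, previous PrEP usage, and current PrEP status"). That list exists to compare the arms, so arm could not be a row in it, and 6.3 never cites it. The better evidence is that 6.2 lists intervention separately from the covariates.

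A reader might also infer that the confidence intervals would be invalid. They would not be. Simulating the literal reading for the 6-month risk difference (60 per arm, 11% missing, 15 imputations), 95% intervals cover the true 6 points about 97% of the time. Root mean squared error is about 5.4 points, against about 6.0 with arm included. The cost is attenuation and power (about 11% versus 17%), in a pilot that reports no formal power calculation.

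Finally, not every departure shrinks the effect. Under long-format defaults the 6-month risk difference rises slightly, to 6.2 points. The DBS link is a separate matter, raised here because the same sentence of 6.3 governs it.

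**Conclusion.** The point holds conditionally and is minor. Taken at its word, 6.3 gives an imputation model narrower than the analysis model. The arm difference then shrinks by about the missing fraction: 6.0 to 5.3 points at 6 months and 9.0 to 8.0 at 3 months. The planned 6-month log-OR loses about 12% to 25%. These figures rest on the 3.3 rates, equal random missingness of 11%, and random-intercept SDs of 1 to 3. The exact factor 1 − m applies to a risk or mean difference with equal missingness; for the odds ratio it is approximate. If dropout depends on earlier adherence, omitting the other visit could also affect the risk difference, by an amount the documents do not let one fix. The case for acting is that the bias is systematic and removable at almost no cost, not that it is large.

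**What to change.** State in 6.3 that imputation is done in wide format, one row per participant. State also that the imputation model for each outcome includes randomised arm, site, the 6.2 covariates (age, relationship status, PrEP usage) and the same outcome at the other visit or visits at which it is measured. Derive imputed binary DBS adherence from the imputed continuous concentration at 1000 fmol/punch, so that the two always agree. Merely removing continuous DBS as a predictor of binary DBS would leave them unlinked.

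The cost is two or three sentences and a predictor matrix, with no new data. The downside is sparse events. Observed non-adherent men would number about 0.89×60×(0.15 + 0.06) = 11.2 at 3 months and 0.89×60×(0.14 + 0.08) = 11.7 at 6 months. With about 53 men observed in the intervention arm, the chance that none is non-adherent is 0.94^53 = 3.8% at 3 months and 0.92^53 = 1.2% at 6 months. Any logistic imputation should therefore be checked for separation. Deriving the binary value from the continuous one avoids the logistic step for the primary outcome.

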# 6. Analysis

#### **6.1 Outcome Definitions**

# **Primary Outcome**

The primary outcome of this study is PrEP adherence, which will be measured objectively using dried blood spot (DBS) testing to detect levels of tenofovir diphosphate (TFVdp). Adherence is defined as achieving a TFVdp concentration of ≥1000 fmol/punch, corresponding to a mean dosing frequency of at least four doses per week. This measure will be evaluated at 3- and 6-months post-randomization. The binary operationalization of this measure will serve as the primary outcome.

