## **Secondary Outcomes**

The secondary outcomes include continuous DBS PrEP adherence, self-reported PrEP adherence (binary and continuous), PrEP knowledge (binary: all questions answered correctly vs. not), PrEP motivation (ordinal categorical), PrEP attitudes and beliefs (continuous), PrEP barriers, PrEP facilitators (continuous), PrEP stigma (continuous), anxiety symptomology (continuous), depression symptomology (continuous), STI diagnoses in the last 6 months (binary: any vs. none), and number of condomless anal sex (CAS) acts with HIV-positive or unknown-status partners in the last 6 months (continuous). For all secondary outcomes, missing data will be recorded and addressed.

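### Imputing the yes/no DBS primary outcome directly by logistic regression pulls imputed adherence too low; impute the TFVdp level and derive the yes/no value from it

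*SAP*

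**What the plan says.** SAP section 6.1 defines adherence as TFVdp at or above 1000 fmol/punch and then fixes the scale: "The binary operationalization of this measure will serve as the primary outcome". The measured level is kept as a secondary outcome: "The secondary outcomes include continuous DBS PrEP adherence, self-reported PrEP adherence (binary and continuous").

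Section 6.3 assumes data missing at random and states that chained equations "will be used to handle missing values for the primary outcome and secondary outcome adjusting all baseline covariates". The method depends on variable type: "predictive mean matching (pmm) for continuous outcomes" and "logistic regression (logreg) for binary outcomes". On the number of imputations it says "Imputations will be generated with 15 datasets".

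Read plainly, the yes/no primary outcome is imputed by logistic regression, and the level it is cut from is imputed by a different method. Section 6.3 does not derive one from the other, limit the number of predictors or deal with sparse data. It does not name arm or the other visit's DBS value as predictors.

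The longest baseline list in the SAP is in section 4.3: "study site, age, sexual identity, outness, relationship status, high school location, ethnicity, education level, occupation, income, previous PrEP usage, and current PrEP status". That is 12 items, several of them naturally multi-category. Section 6.2 gives a shorter set for the analysis model: age, relationship status and PrEP usage, plus site.

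**The concern.** When most men are adherent, a logistic imputation model is fitted to very few non-adherent men. With many predictors its linear predictor becomes noisy, and drawing the coefficients at random adds more noise. Above 50% the logistic curve is concave, so noise on the logit scale lowers the average imputed probability. The result is a downward pull in imputed adherence that does not depend on any failure of the missing-at-random assumption.

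Two things are at stake. The artificial non-adherent values enter both arms and shrink the odds ratio, and the trial is meant to supply preliminary estimates for a later effectiveness trial. In addition, a man with no DBS result is missing both forms at once, so he can be imputed as adherent on the yes/no form with a TFVdp below the cut.

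**Working it through.** **Inputs.** SAP 3.3: 60 men per arm; planning adherence 94% vs 85% at 3 months and 92% vs 86% at 6 months; retention about 89%. SAP 6.3: 15 imputations. SAP section 6.2, Primary Outcome: adjusted odds ratio from a logit GLMM. Assumed, because the documents do not say: the number of covariate parameters (0 to 30 shown), 11% missing at each visit, within-person latent correlation 0.6, and a normally distributed latent DBS level.

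**The plan's own figure.** 0.06 / 0.32 = 0.1875, which rounds to the stated 0.19. From the rates, SD = √[(0.92×0.08 + 0.86×0.14)/2] = 0.311 and 0.06/0.311 = 0.193. The planning rates are therefore reproduced.

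**Non-adherent men available to the imputation model.**
- 3 months: 0.89 × (60×0.06 + 60×0.15) = 0.89 × 12.6 = 11.2
- 6 months: 0.89 × (60×0.08 + 60×0.14) = 0.89 × 13.2 = 11.7

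At 6 months that is 11.7/12 = 0.98 events per parameter with 12 parameters, and 11.7/18 = 0.65 with 18, before arm is counted.

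**Size of the pull.** Simulation of 120 men, 11% missing at random, true adherence about 89%, arm always in the imputation model. The one-visit column used 250 runs per row. The two-visit column also used the other visit as a predictor.

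| Covariate parameters | One visit: points too low | Two visits: points too low |
|---|---|---|
| 0 | 1–2 | – |
| 3 | 3–4 | – |
| 5 | 5 | 7 (24 runs only) |
| 12 | 8–10 | 13 |
| 18 | 11–13 | 18 |
| 24 | 18–20 | 23 |
| 30 | 22–29 | – |

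A separate simulation gave imputed adherence of 85%, 81%, 77% and 74% with 4, 12, 18 and 24 covariates, that is 4, 8, 12 and 15 points low. One truly prognostic covariate does not remove the pull (6–9 points at 12 parameters, 16–17 at 24). Predictive mean matching on the level followed by the cut gave 87–88% in the two-visit runs and 89–90% in the separate simulation.

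**Effect on overall adherence.** Imputed men number 0.11 × 120 = 13.2 per visit. Shift in the overall rate: 0.11 × 8 = 0.9 points; 0.11 × 13 = 1.4; 0.11 × 20 = 2.2. So about 1 to 2 points.

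**Effect on the log odds ratio.** At the 6-month rates, ln(0.92/0.08) − ln(0.86/0.14) = 2.442 − 1.815 = 0.627. If both arms fall by 1 point: ln(0.91/0.09) − ln(0.85/0.15) = 0.579, a loss of 0.05. If both fall by 2 points: ln(0.90/0.10) − ln(0.84/0.16) = 0.539, a loss of 0.09. Simulation with 12 to 24 parameters gives a loss of about 0.02 to 0.09. In the two-visit GLMM, median log odds ratios with logistic imputation were 0.91, 0.91 and 1.15 (12, 18, 24 parameters), against 1.04, 1.20 and 1.27 for available cases and 1.03, 1.18 and 1.19 for the level-then-cut method. Those rest on 57 to 85 runs and are approximate.

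**Effect on precision.** On the log odds ratio scale, the SE with logistic imputation is 0.96–0.99 times the available-case SE. It is 0.97–1.01 times the SE with the level-then-cut method.

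**The case against.** **Precision.** A reader might infer that noisy imputation widens the confidence interval. It does so for a risk difference (SE 1.06 to 1.13 times complete-case), but the SAP estimates an adjusted odds ratio, and on that scale the SE does not grow. The objection stands. The unchanged SE is no reassurance, though, because it partly reflects invented non-adherent events.

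**Predictor count.** A reader might take "primary outcome and secondary outcome adjusting all baseline covariates" to mean all 12 items in section 4.3. Those items are listed as characteristics for description and balance, and section 6.2 names a far shorter covariate set. Under the short reading the pull is about 3 to 5 points. The text supports either reading, so the larger figures are conditional.

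**Small consequence.** A pull of 8 to 13 points in 13.2 imputed men is 1.1 to 1.7 men per visit. In one simulation the mean risk difference was 0.059, against 0.059 in full data with 12 predictors and 0.058 with 18. This stands; the damage is mild attenuation of the odds ratio.

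**Lower adherence.** The planning rates come from a prior SPARK trial. Here PrEP is newly introduced, only interested men receive a prescription, and the analysis is intention-to-treat. At 75% vs 65% the pull is about 2 to 7 points; at 60% vs 50% it is 0 to 1. This also stands.

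**Separate imputation.** A reader might infer that the two DBS forms are imputed in isolation, or that arm is left out. The SAP says neither; it is silent on both. One simulation found the forms disagreeing in 26–32% of imputed men, but only by assuming isolation. If instead the level predicts the yes/no form at the same visit, the relation is deterministic and the logistic fit separates. Neither route guarantees consistency.

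**Fairness of the comparison.** A normal latent level favours predictive mean matching, and shortening the logistic predictor list alone removes much of the pull. Both are true; the shorter list still leaves 3 to 5 points and the consistency problem.

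**Conclusion.** The concern holds in a limited form. As written, section 6.3 imputes the yes/no primary outcome directly from few events and does not link it to the level it is defined by. At the planning rates and 11% missing, imputed adherence is about 8 to 13 points low with 12 to 18 covariate parameters, 3 to 5 with a short list, and 15 or more with 24. The two-visit runs gave larger pulls. The SAP does not fix the parameter count, and the pull shrinks if true adherence is lower than planned.

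These figures must not be read as bias in the trial's adherence rates. Overall adherence moves about 1 to 2 points, and the log odds ratio loses about 0.02 to 0.09 of roughly 0.6. The documents give no support for a wider odds-ratio interval.

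The change is still worth making. Level-then-cut imputation tracks the full-data log odds ratio more closely (root mean squared error 0.22–0.24, against 0.25–0.29) and rules out contradictory pairs. It is a cheap improvement of low to moderate priority.

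**What to change.** In SAP section 6.3:

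- Impute the TFVdp concentration at each visit by predictive mean matching from a short named predictor list: arm, site, the other visit's TFVdp, and the analysis-model covariates (age, relationship status, PrEP usage).
- Derive the yes/no outcome (at or above 1000 fmol/punch) within each imputed dataset, and do not impute it as a variable of its own.
- Handle self-reported adherence the same way: impute the continuous form and derive the binary form.
- Report an available-case GLMM as a sensitivity analysis.

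The cost is SAP wording, a few lines of code, and a stated numeric code for values below the assay limit. No new data are needed, since the TFVdp level is already collected as a secondary outcome.
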